4.3. Protocol Deviations

A listing will be provided for subjects in the Randomized Analysis Set who violated at least 1 inclusion or exclusion criterion. The listing will include the unmet criteria. A listing of subjects who received the wrong study treatment will also be provided.

Protocol deviations occurring after subjects entered the study are documented during routine monitoring. The number and percentage of subjects with important protocol deviations by deviation reason will be summarized by treatment group for the Randomized Analysis Set. A by-subject listing will be provided for those subjects with important protocol deviations.

4.4. Assessment of COVID-19 Impact

This study was ongoing during the novel coronavirus (COVID-19) pandemic which has an impact on the study conduct, including in some cases the disruption in the regular visit schedules. Some subjects were unable to attend onsite visits due to shelter in place guidelines, site closures, or other reasons. This section describes how special situations due to COVID-19 will be handled in the analysis.

4.4.1. Protocol Deviations Due to COVID-19

A by-subject listing will be provided for subjects with important protocol deviations related to COVID-19 if applicable. A separate listing will be provided for subjects with non-important protocol deviations related to COVID-19 if applicable.

4.4.2. Missed and Virtual Visits due to COVID-19

A by-subject listing of subjects with missed or virtual visits due to COVID-19 will be provided by subject ID number in ascending order.

Information regarding missed or virtual visits due to COVID-19 will be collected as free text in the CRF comment fields. The determination of missed or virtual visits due to COVID-19 will be done using Natural Language Processing (NLP) to search the CRF comment fields. A detailed explanation of the algorithm is given in [Appendix 2](#).

5. BASELINE CHARACTERISTICS

5.1. Demographics and Baseline Characteristics

Subject demographic data (eg, age, sex, race, and ethnicity) and baseline characteristics (eg, body weight, height, and body mass index [BMI]) will be summarized by treatment group and overall, using descriptive statistics (sample size, mean, SD, median, Q1, Q3, minimum, and maximum) for continuous data and by the number and percentage of subjects for categorical data. Age is calculated as age in years at the first dose of study drug. The summaries of demographic data and baseline subject characteristics will be provided for the Safety Analysis Set. A by-subject demographic listing will be provided by subject ID number in ascending order.

5.2. Other Baseline Characteristics

The following baseline disease characteristics will be summarized by treatment group and overall using descriptive statistics:

- BMI categories (< 18.5 kg/m² [underweight], $\geq 18.5 - 25.0$ kg/m² [normal], $\geq 25.0 - 30.0$ kg/m² [overweight], and ≥ 30.0 kg/m² [obese])
- HBV DNA (IU/mL)
- HBV DNA categories (< 20 IU/mL, ≥ 20 to < 69 IU/mL, ≥ 69 IU/mL)
- ALT (U/L)
- ALT level based on central laboratory normal range (\leq upper limit of normal [ULN], $> ULN - 5 \times ULN$, $> 5 \times ULN - 10 \times ULN$, $> 10 ULN$)
- ALT level based on 2018 American Association for the Study of Liver Diseases (AASLD) normal range with the ULN as 25 U/L for female and 35 U/L for male ($\leq ULN$, $> ULN - 5 \times ULN$, $> 5 \times ULN - 10 \times ULN$, $> 10 ULN$)
- Estimated GFR by CG (mL/min), CKD-EPI creatinine (mL/min/1.73 m²), CKD-EPI Cystatin C (mL/min/1.73 m²) and Cr EDTA (mL/min/1.73 m²) methods
- Chronic kidney disease (CKD) stage by estimated GFR by CG, CKD-EPI creatinine, CKD-EPI Cystatin C and Cr EDTA methods
- HBeAg status (positive, negative)
- HBeAb status (positive, negative)
- HBsAg status (positive, negative)
- HBsAb status (positive, negative)

- Previous TDF use experience (yes, no) and TDF use at Day 1
- Previous Lamivudine use experience (yes, no) and Lamivudine use at Day 1
- Years positive for HBV
- Years of liver transplant
- Fibrotest score
- Fibrosis stage by fibrotest score (0 - 0.48, 0.49 - 0.74, 0.75 - 1)
- Proteinuria by urinalysis (dipstick) (Grade 0, Grade 1, Grade 2, Grade 3)
- Vitamin D
- Clinical BMD status (normal, osteopenia, osteoporosis)
- Hip fracture and major osteoporotic fracture probabilities estimated using FRAX[®] (see Section 7.3.4)

The stages of CKD by estimated GFR are defined as follows:

- **Stage 1:** ≥ 90
- **Stage 2:** ≥ 60 and < 90
- **Stage 3:** ≥ 30 and < 60
 - **Stage 3a:** ≥ 45 and < 60
 - **Stage 3b:** ≥ 30 and < 45
- **Stage 4:** ≥ 15 and < 30
- **Stage 5:** < 15

A by-subject listing of other baseline characteristics will be provided by subject ID number in ascending order.

5.3. Medical History

A listing of medical history data will be provided for the Randomized Analysis Set.

6. EFFICACY ANALYSES

6.1. Primary Efficacy Endpoint

The analysis of the primary efficacy endpoint was performed previously; this analysis will also be repeated in the Final Analysis for completeness.

6.1.1. Definition of the Primary Efficacy Endpoint

The primary efficacy endpoint is the proportion of subjects with HBV DNA < 20 IU/mL at Week 24.

6.1.2. Analysis of the Primary Efficacy Endpoint

The primary efficacy analysis will be conducted after the last randomized subject reaches Week 24 or discontinues study drug prematurely. A Missing = Failure (M = F) approach will be employed. In this approach, all missing data will be treated as not achieving the primary endpoint (ie, having HBV DNA \geq 20 IU/mL).

6.1.3. Secondary Analysis of the Primary Efficacy Endpoint

Sensitivity analyses will be performed for the primary endpoint using Missing = Excluded (M = E) approach. In this approach, all missing data will be excluded in the computation (ie, missing data points will be excluded from both the numerator and denominator in proportion computation).

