## 6.6. Criteria for Discontinuation of Study Treatment

Study medication may be discontinued in the following instances:

- Intercurrent illness that would, in the judgment of the investigator, affect assessments of clinical status to a significant degree. Following resolution of intercurrent illness, the subject may resume study dosing at the discretion of the investigator.
- Unacceptable toxicity, as defined in the toxicity management section of the protocol, or toxicity that, in the judgment of the investigator, compromises the ability to continue study-specific procedures or is considered to not be in the subject's best interest
- Subjects with confirmed  $eGFR_{CKD-EPI}$  of  $< 15 \text{ mL/min/1.73m}^2$  at any time during the study will have their study drug permanently discontinued
- Lack of efficacy (virologic failure)
- HBsAg loss with seroconversion to anti-HBs. These subjects should discontinue study drug within 3-6 months following confirmation of seroconversion to anti-HBs. Subjects with HBsAg loss with confirmed seroconversion before Week 48 are not permitted to discontinue study drug prior to the Week 48 visit
- Discontinuation of study drug for subjects experiencing HBsAg-loss with confirmed seroconversion to anti-HBs, who have known bridging fibrosis or cirrhosis, should be considered on a case by case basis
- Subject request to discontinue for any reason
- Subject noncompliance
- Pregnancy during the study; refer to [Appendix 6](#)
- Discontinuation of the study at the request of Gilead, a regulatory agency or an institutional review board or independent ethics committee (IRB/IEC)

CCI

CCI

CCI

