1.2. Study Design

This is a randomized, open-label, single center Phase 2 study to evaluate the safety and efficacy of TAF 25 mg QD versus TDF in adult chronic hepatitis B (CHB) infection subjects with Stage 2 or greater chronic kidney disease and have previously received a liver transplant.

Treatment Groups

Approximately 50 subjects will be randomized 1:1 to either continue current treatment regimen with TDF (alone or in combination with other approved antivirals) or to receive TAF 25 mg orally daily. Approximately 40 of 50 subjects were to be enrolled with $eGFR_{CKD-EPI} < 60$ ml/min/1.73m². Randomization was stratified by screening renal function ($eGFR_{CKD-EPI} < 50$ ml/min/1.73m² and ≥ 50 ml/min/1.73m²)

- **Treatment Arm A:** approximately 25 subjects administered TAF 25 mg oral daily
- **Treatment Arm B:** approximately 25 subjects to continue administration of TDF alone or in combination with other approved antivirals as per local practice

Key Eligibility Criteria

Subjects were to have met the following key eligibility criteria:

- Documented evidence of chronic HBV infection prior to transplantation
- Primary or secondary (re-transplant), liver alone or liver and kidney transplant recipient from deceased or living donor
- Liver Transplant ≥ 12 weeks prior to screening
- Maintained on TDF alone or in combination with other approved antivirals for HBV prophylaxis or treatment
- Have been on approved HBV oral antiviral (OAV) treatment for at least 12 weeks post-transplant prior to screening, with HBV DNA $<$ lower limit of quantitation (LLOQ) at screening
- Screening $eGFR_{CKD-EPI} < 90$ ml/min/1.73m²

Study Periods/Phases

The duration of the study treatment is 48 weeks with an initial screening period of 45 days. Subsequent to Screening, subjects will be randomized to receive TAF or TDF alone or in combination with approved antivirals per local practice.

CCI

If subjects CCI choose to not continue or discontinue TAF prematurely, they will be followed for 24 weeks after the discontinuation of study treatment (ie, Treatment Free Follow-Up, TFFU) or until an alternative CHB treatment is started, whichever occurs first. In this SAP, the first 48 weeks of study treatment is referred to as randomized phase, CCI

Schedule of Assessments

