3.7.2. Analysis Visit Windows

Subject visits might not occur on protocol-specified days. Therefore, for the purpose of analysis, observations will be assigned to analysis windows.

The following windows (Table 3-1 to Table 3-5) apply to baseline and on-treatment assessments only. For summaries and analysis, assessments will first be categorized into baseline and on-treatment assessments occurring during the randomized CCI phase, before applying analysis windows.

For subjects who prematurely discontinued the randomized study drug CCI, laboratory assessments up to and including the last dose date of the randomized study drug + 3 days, and DXA assessments up to and including the last dose date of the randomized study drug + 14 days, will be considered as baseline or on-treatment during the randomized phase.

CCI

For subjects who have not discontinued the randomized study drug permanently, data collected up to database finalization date will be considered as baseline or on-treatment of the randomized phase.

CCI

CCI
 CCI

For subjects who discontinue study drug early due to HBsAg loss with confirmed seroconversion, all efficacy data including data collected after the last dose date of the study drug will be reassigned analysis visits using the on-treatment assessment windows (Table 3-1 and Table 3-3).

The analysis windows for HBV DNA, hematology, serum chemistry and liver function tests, eGFR (by CG and CKD-EPI), renal biomarkers urine albumin to creatinine ratio (UACR), urine protein to creatinine ratio (UPCR), renal tubular maximum reabsorption rate of phosphate to the glomerular filtration rate (TmP/GFR), urine fractional excretion of filtered phosphate (FEPO₄), fractional excretion of uric acid (FEUA), non-fasting glucose, weight, and vital sign assessments are provided in Table 3-1.

Table 3-1. Analysis Visit Windows for HBV DNA, Hematology, Serum Chemistry and Liver Function Tests, eGFR (by CG and CKD-EPI), UACR, UPCR, TmP/GFR, FEPO₄, FEUA, Non-fasting Glucose, Weight, and Vital Sign Assessments

Nominal Visit	Nominal Study Day	Lower Limit	Upper Limit
Baseline			1
Week 4	28	2	41
Week 8	56	42	69
Week 12	84	70	111
Week 20	140	112	153
Week 24	168	154	209
Week 36	252	210	293
Week 48	336	294	377 (419 ^b)

[figure not shown]
CCI
 CCI

^b Applies to UACR, UPCR, TmP/GFR, FEPO₄ and FEUA only.

The analysis window for Fasting Glucose, Serum Cystatin C and eGFR by CKD-EPI Cystatin C is in Table 3-2.

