6.2.2. Analysis Methods for Secondary and Other Efficacy Endpoints

All the secondary and other efficacy endpoints involving proportions will be analyzed using the same statistical method (M = F) applied to the analysis of the primary efficacy endpoint. Sensitivity analyses will be performed using the M = E approach as well.

In addition, the proportion of subjects with HBV DNA < 20 IU/mL and the proportion of subjects with normal ALT (by central laboratory and AASLD criteria, M = F) will be separately plotted with 95% CI over time for FAS. Median (Q1, Q3) and mean (95% CI) of change from baseline in ALT (U/L) will also be plotted over time using observed data for FAS.

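### The Missing = Excluded sensitivity analysis of the HBV DNA endpoints drops subjects who stopped for virologic failure too early to have an in-window value

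*SAP*

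**What the plan says.** SAP 6.1.1 defines the endpoint: "The primary efficacy endpoint is the proportion of subjects with HBV DNA < 20 IU/mL at Week 24". SAP 6.1.2 sets the primary rule, M = F, under which "all missing data will be treated as not achieving the primary endpoint". SAP 6.1.3 adds one sensitivity analysis, M = E, under which "missing data points will be excluded from both the numerator and denominator in proportion computation". SAP 6.2.2 carries both rules to the Week 48 HBV DNA endpoint and to the ALT proportions: "Sensitivity analyses will be performed using the M = E approach as well".

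Three other provisions decide who has a missing value:

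- Protocol 6.6 lists virologic failure among the reasons for which study drug may be stopped.
- SAP 3.7.2 says that, for subjects who stop randomized drug early, "laboratory assessments up to and including the last dose date of the randomized study drug + 3 days" count as baseline or on-treatment. The visit windows apply to that data only, and later data are post-treatment.
- SAP 3.7.2 makes one exception. If drug is stopped for HBsAg loss with confirmed seroconversion, efficacy data collected after the last dose are put back into the on-treatment windows. The visible text has no matching provision for virologic failure.

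**The concern.** A missing-data sensitivity analysis should vary the assumption about outcomes that are unknown. Here one kind of missing value is not unknown. A subject whose HBV DNA rebounds and who stops drug for that reason has lost suppression on the assigned regimen, and the value is missing only because the data cut-off closes before the window opens. M = E treats this subject in the same way as someone lost to follow-up for unrelated reasons.

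The resulting error runs in one direction. It can only raise the M = E response rate, and only in an arm where the regimen has failed someone. M = E is also the only missing-data sensitivity analysis that the SAP names for these endpoints. With about 25 subjects per arm, a single case moves the percentage by several points, and a gap between M = F and M = E would not by itself show whether it came from neutral dropout or from virologic failure.

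**Working it through.** The documents give no expected response rate or sample size calculation for this trial, so there is no stated figure to reproduce.

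**Inputs**
- Arm size: about 25 each (SAP 1.2: "approximately 25 subjects administered TAF 25 mg oral daily", and likewise for TDF).
- HBV DNA windows (SAP Table 3-1): Week 24 is Days 154 to 209; Week 48 opens at Day 294.
- On-treatment cut-off after an early stop: last dose + 3 days (SAP 3.7.2).
- Context: Protocol Table 1-2, the two Phase 3 studies.

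**Step 1. Who has no in-window value.** A value is impossible if last dose + 3 falls before the window opens.
- Week 24: 150 + 3 = 153 < 154, so a last dose on or before Day 150 leaves none.
- Week 48: 290 + 3 = 293 < 294, so a last dose on or before Day 290 leaves none.

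A last dose on Day 151 or later can still leave a Week 24 value. If that value is >= 20 IU/mL, the subject is a failure under both rules. So is a subject who is viremic and still on drug.

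**Step 2. Effect on the proportion.** With n subjects, s suppressed and m missing, M = F is s/n and M = E is s/(n − m). Exact (Clopper-Pearson) 95% intervals are in brackets.
- One failure, stopped early, all others suppressed: M = F 24/25 = 96.0% (79.6 to 99.9); M = E 24/24 = 100% (85.8 to 100).
- Two failures, both stopped early: M = F 23/25 = 92.0%; M = E 23/23 = 100%.
- Two failures, one of them with an in-window value: M = F 23/25 = 92.0%; M = E 23/24 = 95.8%.
- Arms of 24 or 26 with one early failure: 95.8% or 96.2% becomes 100%.

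**Step 3. Effect of the fix.** In the one-failure case, counting the lack-of-efficacy stop as a failure gives 24/25 = 96.0% under M = E.

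**Step 4. How often this might happen.** In Table 1-2, stops for lack of efficacy number 0 + 0 + 1 + 0 = 1 among 285 + 140 + 581 + 292 = 1298 subjects. That is 1 of the 10 + 6 + 27 + 9 = 52 without Week 48 virologic data. At that rate the chance of at least one such stop in 25 subjects is 1 − (1 − 1/1298)^25 = 1.9%. The Phase 3 population differs from this post-transplant one, so the table gives a range under assumed rates, none of which comes from the documents:

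| Assumed rate of stopping for lack of efficacy | Chance of at least one in 25 |
|---|---|
| 0.5% | 12% |
| 1% | 22% |
| 2% | 40% |
| 4% | 64% |

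These are chances of any such stop. Only those early enough to meet Step 1 affect M = E.

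**The case against.** The strongest case against is that the plan already handles this where it matters. M = F is the primary rule and counts every early stop as a failure, and showing M = F beside M = E displays the effect of missing data. SAP 4.1 summarises reasons for stopping randomized treatment by arm and lists them by subject, so each case can be identified in a trial of this size. The study is exploratory and descriptive, and no margin or decision depends on M = E. All of this is true and limits the point to the sensitivity analysis. It does not correct the M = E estimate, because the disposition summary is not tied to the endpoint. The Protocol 8.3 statement that sensitivity analyses will be done as warranted does not specify another one.

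A reader might infer three stronger things that the documents do not support.
- That M = E removes virologic failures as a class. It removes missing values; failures with an in-window value stay in, and Protocol 6.6 permits stopping without requiring it.
- That the primary result is inflated. It is not.
- That a rise to 100% is to be expected. It is a constructed case.

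Two practical objections also stand. The Week 24 and Week 48 analyses have already been run (SAP 2.1.2, 2.1.3), so any change comes after open-label data were analysed. And an HBV DNA criterion must not be used to score ALT endpoints.

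Redaction is a further limit. Protocol 6.7 and 6.8 are blacked out, as is part of the opening condition of the last dose + 3 days rule, so any related provision there cannot be checked. The M = E rule itself is fully visible.

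**Conclusion.** The point holds for the M = E analyses of HBV DNA < 20 IU/mL at Weeks 24 and 48 and goes no further. As written, M = E discards a known failure when the subject stopped for virologic failure with a last dose on or before Day 150 or Day 290 respectively. In an arm of about 25, one such subject among otherwise suppressed subjects separates the two rules by 4.0 percentage points (96.0% v 100%). Week 48 is the more exposed endpoint, because its cut-off is 290 − 150 = 140 days later.

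This rests on the last dose + 3 days rule applying to these subjects as its visible text reads. Whether anyone is affected is unknown, and Phase 3 experience makes zero quite possible. It is a cheap improvement to a sensitivity analysis and no threat to the primary conclusion.

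**What to change.** In SAP 6.1.3, and in 6.2.2 for the Week 48 HBV DNA endpoint only, state that M = E counts as failures subjects without an in-window value who discontinued for lack of efficacy, or whose last on-treatment HBV DNA before discontinuation was >= 20 IU/mL. Only the remaining missing values are excluded. Tabulate missing values by reason and arm, as Protocol Table 1-2 did for Phase 3. Leave M = E for the ALT proportions as it is.

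The cost is about one sentence and one small table. Discontinuation reasons and HBV DNA at each visit are already collected, and SAP 6.1 and 6.2 repeat these analyses in the Final Analysis. There are two small downsides. A single unconfirmed value just above 20 IU/mL before an unrelated dropout would count as a failure. And because results have already been produced, the change must be recorded as a revision (SAP 1 provides for documenting later changes in the clinical study report), with the M = E result as now specified shown alongside.

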6.2. Other Efficacy Endpoints

The analysis of the secondary and other efficacy endpoints at Weeks 24 and 48 was performed previously; the analysis will also be repeated in the Final Analysis for completeness.

6.2.1. Definition of Secondary and Other Efficacy Endpoints

The secondary efficacy endpoint is:

- The proportion of subjects with plasma HBV DNA < 20 IU/mL at Weeks 48

Other efficacy endpoints include:

- The proportion of subjects with normal ALT (by central laboratory and AASLD criteria) at Weeks 24 and 48
- The proportion of subjects with ALT normalization (by central laboratory and AASLD criteria) at Weeks 24 and 48

- The change from baseline in ALT at Weeks 24 and 48

ALT normalization is defined as ALT > ULN (by central laboratory normal range or 2018 AASLD normal range) at baseline but within normal range at a postbaseline visit

6.2.2. Analysis Methods for Secondary and Other Efficacy Endpoints

All the secondary and other efficacy endpoints involving proportions will be analyzed using the same statistical method (M = F) applied to the analysis of the primary efficacy endpoint. Sensitivity analyses will be performed using the M = E approach as well.

In addition, the proportion of subjects with HBV DNA < 20 IU/mL and the proportion of subjects with normal ALT (by central laboratory and AASLD criteria, M = F) will be separately plotted with 95% CI over time for FAS. Median (Q1, Q3) and mean (95% CI) of change from baseline in ALT (U/L) will also be plotted over time using observed data for FAS.

6.3. Changes from Protocol-Specified Efficacy Analyses

Change from baseline in ALT was added in the SAP as other efficacy endpoints to fully explore the treatment effect of TAF versus TDF. Proportion of normal ALT and ALT normalization by visit evaluated using central laboratory and 2018 AASLD ULN were also added.

The Randomized Analysis Set was not defined in the protocol but is added in the SAP.

7. SAFETY ANALYSES

For the final safety analysis, exposure and cumulative safety data (treatment-emergent AEs, treatment-emergent laboratory abnormalities, etc) will be summarized for the randomized phase based on the Safety Analysis Set, CCI [REDACTED]

By-visit summary tables will be presented for the entire study treatment period (randomized CCI [REDACTED]), based on subjects in the Safety Analysis, starting from the randomized phase baseline.

CCI [REDACTED]

7.1. Adverse Events and Deaths

7.1.1. Adverse Event Dictionary

Clinical and laboratory AEs will be coded using the current version of MedDRA. System organ class (SOC), high-level group term (HLGT), high-level term (HLT), preferred term (PT), and lower-level term (LLT) will be provided in the AE dataset.

7.1.2. Adverse Event Severity

AEs are graded by the investigator as Grade 1 (mild), Grade 2 (moderate), Grade 3 (severe) or Grade 4 (life threatening) according to toxicity criteria specified in Appendix 5 of the clinical study protocol. The severity grade of events for which the investigator did not record severity will be categorized as “missing” for tabular summaries and data listings, and will be considered the least severe for the purposes of sorting for data presentation.

